### 8.3.4 Describe single catheter PVAC GOLD utilization in persistent AF

Single PVAC GOLD utilization data will be shown for all documented procedures combined (patient level). Also, single PVAC GOLD utilization will be provided for first documented procedures, additional procedures, regular cases and training cases, separately.

Single catheter PVAC GOLD utilization means here, that only PVAC GOLD was used during the procedure, regardless of using sheaths. No adjunctive devices were used. For this ancillary objective, only patients with persistent AF will be analysed.

The parameters of interest are:

- Phased RFA catheters used during the procedure
- Indication for Phased RFA
- Location of linear lesions or substrate modifications
- Atrial CV
- AF/ left Afl recorded on ECG/EGM
- AF re-ablations

**Table 12:** PVAC GOLD utilization variables from baseline and procedure form

Objective section	Definition (used variables)	Related FID's annotated eCRF (V1.3, V1.4)
Phased RFA catheters used during the procedure	General number of catheters used Phased RFA catheters used Other (free text field)  From procedure form	F2100005  F2100010 F2100020
Indication for Phased RFA	Indication to schedule Phased RFA (AF type)  If "Persistent AF"  From baseline form	F10000110  F10000113
Location of linear lesions or substrate modifications	Were any non-PVI lesions performed  Substrate Modification = Lines  Location  From procedure form	F20001010  F20001040  F20001020

Atrial CV	Cardioversion(s) for AF in the last 12 months Latest date of CV(s) specify CV  From baseline form	F13000710 F13000720 F13000740 F13000750 F13000770
-----------	---	---

### 8.3.5 Evaluate QoL (AFEQT) dynamic at 12 month FU

Quality of Life analysis will be done for all available subjects. Therefore, completed AFEQT questionnaire at baseline and at 12 month FU will be used. With it, single scales and AFEQT score will be analysed at baseline and at 12 months. Also, absolute and relative differences in AFEQT score between baseline and 12 months will be displayed. Score calculations are described in SAP chapter 7.4.3, rules for analysis in SAP chapter 6.3.

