- Treated with the PVAC GOLD catheter only in persistent AF patients

Evaluate QoL (AFEQT) dynamic through 12 months.

Rational: Symptom relief and improvement in QoL are the major therapeutic goals of PVI. The validated AFEQT questionnaire designed specifically to assess the impact of AF burden on patient's QoL. Improvement in QoL will be used as a subjective indicator of Phased RFA long term success.

Endpoint definition: AFEQT questionnaire completed at baseline and at 12 months FU.

Analysis Methods: Change in QoL from baseline to 12 months will be summarized using mean, SD, minimum, median, maximum and IQR. Statistically significant change from baseline will be assessed using a two-sided t-test.

Limitations: If QoL was completed at baseline, but missed for 12 months FU, this patient will be excluded from the analysis. As far as QoL is not a standard of care in some hospitals it is up to patient consideration to complete or to refuse QoL completing.

5 Project Termination

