### 7.1 Definitions

#### Pre-post differences

Pre-post differences in absolute values (also called absolute changes) will always be calculated as post-baseline value minus baseline value.

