#### Relative pre-post differences

Relative pre-post differences (also called percent changes) will always be calculated as  $100\% \text{ (post-baseline value minus baseline value) / baseline value}$ .

Pre-post differences will be calculated for the following variables (other can be proposed retrospectively):

**Table 2:** Variables for pre-post differences

Variables	Pre- value	Post- value	Derived variables
Antiarrhythmic medication Anticoagulation medication Antiplatelets Other cardiovascular medication	Discharge	12MFU visit/ 12MFU by phone	Number of patients 
 
• Never on
 
• Newly on
 
• Continued
 
• Discontinued
 

AFEQT-Score	Baseline	12MFU/ 12MFU by phone	Absolute change in AFEQT score
AF burden	Baseline	12MFU visit/ 12MFU by phone	Absolute change in AF burden [%]
EHRA AF symptoms classification	Baseline	12MFU visit/ 12MFU by phone	

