## 7.2 Handling data entity types

The CDISC data export is arranged according to the tables in the eCRF (see Data Management Plan). These tables contain data of entities, whose definitions only partially correspond to the entity types processed in statistical analysis. The aim of the analysis is to show the data at patient level.

The following entity types can be used for statistical analysis:

1. Patient
2. Procedure
3. Follow-up
4. Adverse Event

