# 8 Descriptive Statistics

This section describes the most relevant parts of the statistical analyses planned for this registry. All planned statistical methods will be described in detail in the Statistical Analysis Plan, which should be finalized prior to interim analysis and need to be finalized prior final analysis.

In general, this registry is intended to collect data under real life conditions. The statistical analysis will be performed in explorative and descriptive manner, i.e. no pre-specified hypothesis testing.

All variables collected in the CRF as well as the data obtained from the QoL assessments and all derived parameters will be used in the statistical analysis.

Binary, categorical, and ordinal parameters will be summarized by means of absolute and percentage numbers within the various categories.

Continuous data will be summarized by means of standard statistics, i.e. number of available data, number of missing data, mean, standard deviation, minimum, median, maximum, 5th and 95th percentile, lower and upper quartile (see SAP Appendix A).

Time-to-event data is planned to be analysed via a Cox proportional hazard regression model presenting hazard ratios and the corresponding 95% CI. In addition, Kaplan-Meier

curves may be presented for the time-to-event data. Two-sided 95%-CI will be presented for important parameters, but should be interpreted in an exploratory descriptive way. No formal statistical tests are planned within the statistical analysis. Event rates will be calculated for 3, 6, 9 and 12 months after first documented procedure and may be displayed graphically.

To measure statistical differences in continuous or dichotomous/ multinomial variables between baseline and 12 month FU non-parametric (e.g. Friedman's Chi-Square Test, McNemar's Test) will be utilized. The test is only performed if the variable is not missing at admission and discharge.

A biometrical report including descriptive statistics of all relevant documented parameters will be generated for the overall patient population as well as for each participating country (SAP chapter 8.7). Depending on the variable(s) of interest, additional selection criteria for subjects (e.g. subgroup analyses) considered in specific analyses may be used, if considered useful during the statistical analysis (SAP chapter 8.6).

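### Averaging individual percent changes in AFEQT generally gives an inflated figure; SAP 8.3.5 should rest on the absolute change (minor, ancillary objective)

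*SAP*

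**What the plan says.** SAP 8.3.5 analyses the AFEQT scales and score at baseline and 12 months and adds: "Also, absolute and relative differences in AFEQT score between baseline and 12 months will be displayed". SAP 7.1 gives both definitions. The absolute difference "will always be calculated as post-baseline value minus baseline value". For the other, "Relative pre-post differences (also called percent changes) will always be calculated as" 100% times that difference, divided by the baseline value.

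Neither section says outright that the percentage is formed patient by patient and then averaged, but that is the natural reading. SAP 7.2 says "The aim of the analysis is to show the data at patient level", and SAP 8 summarises continuous data by "number of available data, number of missing data, mean, standard deviation, minimum, median, maximum", plus quartiles and percentiles.

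The derived variable that SAP Table 2 lists for this score is "Absolute change in AFEQT score". Protocol 4.4.3 says "Change in QoL from baseline to 12 months will be summarized using mean, SD, minimum, median, maximum and IQR" and plans a two-sided t-test of change from baseline. It mentions no percent scale. The SAP does not say which summary leads and has no rule for a baseline score of 0.

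**The concern.** AFEQT runs from 0 (worst) to 100. Dividing by the patient's own baseline gives unequal weight to equal and opposite movements. A patient going from 40 to 60 counts as +50%, and one going from 60 to 40 as -33.3%. Together they average 0 points but +8.3%. So zero is not, in general, the value that the mean percent change takes when the group as a whole has not moved.

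This matters because the protocol gives the result a meaning: "Improvement in QoL will be used as a subjective indicator of Phased RFA long term success". The registry has no control arm in which the same artefact would appear and cancel. A mean percent improvement quoted alone would overstate the benefit. Across subgroups with different baseline scores it would also show different benefits for the same gain in points.

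**Working it through.** **Inputs.** The formulas come from SAP 7.1 and the 0-100 scale from SAP 7.4.3. The documents give no AFEQT mean, SD, correlation between visits or expected gain. These are therefore assumed: mean 45-65, SD 15-20, correlation ρ 0.3-0.9. The plan has no figure of its own to reproduce.

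**Direction of the bias.** Let X be the baseline and Y the 12-month score. The mean percent change is 100 × (E[Y/X] − 1). If X and Y are exchangeable, E[Y/X] = E[(Y/X + X/Y)/2] ≥ 1, with equality only if Y = X in every patient.

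**Approximate size.** With equal means, a second-order expansion gives CVx × (CVx − ρ × CVy), where CV is SD/mean. With equal SDs this is CV² × (1 − ρ). For mean 55, SD 20, ρ = 0.5: (20/55)² × 0.5 = 0.132 × 0.5 = 6.6%. This understates the bias, because low baselines contribute very large ratios.

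**Simulation with no change in distribution.** Scores were drawn from beta distributions on 0-100, rounded to the steps of a 20-item score and paired by a Gaussian copula, with 200,000 pairs per setting. Mean percent change:

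| Mean, SD | ρ = 0.3 | ρ = 0.5 | ρ = 0.7 | ρ = 0.9 |
|---|---|---|---|---|
| 45, 15 | +10.9 | +7.7 | +4.5 | +1.6 |
| 45, 20 | +27.8 | +19.1 | +11.0 | +3.7 |
| 55, 15 | +7.1 | +4.9 | +3.0 | +1.0 |
| 55, 20 | +16.8 | +11.7 | +7.0 | +2.2 |
| 65, 15 | +5.0 | +3.6 | +2.1 | +0.8 |
| 65, 20 | +11.9 | +8.5 | +5.1 | +1.7 |

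In every cell the mean absolute change is 0 to within 0.1 point, the median percent change is 0, and the percent change of the group means is 0 to within 0.2%. At ρ = 1, where no patient changes, the mean percent change is exactly 0.

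**When the sign reverses.** With equal means, the approximation turns negative when ρ × SD at 12 months exceeds the baseline SD.
- Mean 65, SD 12 then 18, ρ = 0.9: 0.9 × 18 = 16.2 > 12. Simulated: -1.4%.
- Mean 55, SD 15 then 20, ρ = 0.9: 0.9 × 20 = 18 > 15. Simulated: -2.0%.
- The same two pairs of SDs at ρ = 0.5: +1.1% and +3.2%.

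**With a real gain of 15 points** (SD 18, ρ = 0.5):
- Baseline mean 45: the group means rise by 15/45 = 33.3%. The mean of individual percent changes is about +55%, or 22 percentage points more.
- Baseline mean 65: the group means rise by 15/65 = 23.1%. The mean of individual percent changes is about +32%, or 9 percentage points more.

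So the overstatement itself depends on where the group starts.

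**Baseline of 0.** A score of 0 needs every answered item at level 7, because 100 − (7n − n) × 100/(6n) = 0. In the simulations at most 0.003% of baselines were 0. In 800 patients that is 800 × 0.00003 = 0.024 patients.

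**The case against.** The strongest reply is that this is one supplementary display on an ancillary, descriptive objective, and that the reader is not left with the percentage alone. The absolute change stands beside it. SAP 8 also reports the median, which was 0 in every equal-distribution setting above. Both points stand, and they limit the harm. They do not remove it: the SAP does not make either figure lead, and nothing warns the reader that zero is not the reference value for the mean percent change.

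Four stronger readings are tempting, and the documents do not support them.

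- **The mean percent change is always positive without an effect.** It is zero if no patient changes, and it can be slightly negative, as shown above.
- **A significance test would falsely declare improvement.** Neither document specifies a test of mean percent change against zero. The protocol's t-test is on change from baseline. For baseline against 12 months SAP 8 names non-parametric tests, with Friedman's as an example. With two time points that test uses only the direction of each patient's change, which division by a positive baseline leaves unaltered.
- **SAP 8.3.5 contradicts Table 2.** The text introducing Table 2 allows further variables to be proposed later, so the list is open. The two places differ but do not conflict.
- **The formula drops the worst-off patients.** It is undefined at a baseline of 0, but such a score is effectively absent under the assumed distributions.

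It is also fair to say that a fixed gain is by definition a larger percentage of a lower baseline. That part is arithmetic, not bias. The further inflation from averaging ratios, 22 against 9 percentage points in the example, is bias.

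**Conclusion.** The point holds as a minor one. Read in the natural way, SAP 8.3.5 with 7.1 and 8 produces a mean of individual percent changes. That mean is generally biased upward when scores vary within patients: about +2% to +28% with an unchanged score distribution at correlations of 0.3-0.7, falling to about +1% to +4% at 0.9. With a real gain it overstates the percentage, for example about +55% against 33%.

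These sizes rest on assumed means, SDs, correlations and distribution shape, and on percentages being formed per patient before averaging. A reader might infer that the registry would report a quality-of-life improvement where none exists. The documents do not support that, because the same output would show an absolute change and a median percent change at or near zero. The sample size and the main objective are not affected.

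**What to change.** In SAP 8.3.5, remove the relative difference. Report the mean absolute AFEQT change with its 95% CI, and base quality-of-life statements and subgroup comparisons on it. This matches the measure in the protocol and the variable named in Table 2.

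If a percentage is wanted, report the percent change of the group means in patients with both scores, 100 × (mean at 12 months − mean at baseline) / mean at baseline, and state that individual percent changes are not averaged.

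The cost is a one-sentence change to the SAP, with no new data. The only loss is a percent figure that would usually look more favourable.

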## 8.4 Interim analysis

Interim analysis (see CIP Version 2.0), based on study data reported prior to the final report, may be completed and utilized for publication. After documenting all intended first documented procedures and pass the query solving process for baseline data, interim database lock will be used to set a locked data set for this analysis. Analysis sets, analysis tables and predefined comparison groups for interim analysis are displayed in Appendix B and D. Ancillary objectives (SAP chapter 8.3.1 to 8.3.4) will be calculated for this data status. Besides, all other parameters from baseline and first documented procedure will be shown. For details see Appendix B. Data analysis will be in descriptive manner. No adjustments for alpha are necessary as no hypotheses are being tested.

## 8.5 Final analysis

At the end of this study and after the final data base lock, final tables including study objectives (Appendix B), subgroup analysis, comparison group analysis, graphical analysis and benchmark analysis will be performed. Data analysis will be in descriptive manner. No adjustments for alpha are necessary as no hypotheses are being tested.

## 8.6 Analysis of group comparisons and subgroups

To evaluate special subjects, predefined subgroup analysis and predefined group comparisons will be performed. Subgroup and group comparisons will be done at the end of this study. If needed, further analysis can be carried out.

### 8.6.1 Analysis of subgroups

Descriptive subgroup reports will be listed in Appendix C.

## 8.6.2 Analysis of comparison groups

Group comparison will be provided including non-parametric statistical tests and odds ratios with 95% CI (two-group comparison) for all parameters. In Appendix D descriptive reports are listed.

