### 3.3 Sample Size Determination

The sample size calculation is based on the main objective to document real life mid-term efficacy of patients with atrial fibrillation who were scheduled for phased RF ablation. Efficacy is in this case assumed as the proportion of redo ablations 12 months after treatment.

The table below shows the sample size needed for estimating a binomial proportion for given prevalence with corresponding precision.

**Table 1:** Cross table for precision and prevalence for sample size assessment.

Prevalence	Precision			
	1%	2.5%	5%	10%
0.1	4150	665	167	42
0.2	7377	1181	296	75
0.3	9682	1550	388	98

Precision = half-width of a 95% CI

Design effect = 1.2 (variance inflation due to cluster sampling design)

Low sampling rate assumed to have no impact on sample size calculation

Assuming a prevalence of re-ablation 12 months after treatment of 20%, a sample size of 800 will allow the study to estimate the prevalence with a given precision of  $\pm 3.8\%$  [range of 95%-CI: 7.6%]. This size guarantees sufficient information to estimate the prevalence in smaller subgroups (e.g. subgroup with a prevalence of 25% with a precision of  $\pm 6.6\%$  [range of 95%-CI: 13.3%]).

A drop-out rate of 25% is assumed (i.e. an estimated drop-out of about 200 patients). Thus, it is planned to enrol a total number of patients of at least 800 - 1000.

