#### Step 1: Validated and not validated AFEQT language versions

The following language versions used in this registry are validated: French, German, Italian, Spanish, Polish, Dutch, English and Korean. The following language versions used in this registry are not validated: Georgian, Greek, Hungarian, Hebrew, Arabic, Russian and Portuguese.

To evaluate whether validated and not validated language versions differ from each other, baseline AFEQT scores will be compared between both groups, i.e. evaluation of homogeneity of both distributions (Wilcoxon-Mann-Whitney test, two tailed,  $p<0.05$ ). It will be assumed, that both patient sets are equal in their medical history. Further predictors or confounders will not be considered. If the difference proves to be statistically significant, data derived from not validated language versions will be excluded from further analyses. Otherwise, step 2 will be evaluated.

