## 8.7 Benchmark reports

The benchmark reports are a comparison of one single unit (site or country) to the entire group of all other participating units. These benchmark reports are designed to be used as quality control for the participating sites and to describe country differences. Benchmark reports will be provided for:

- Participating site vs. all other sites
- Participating country vs. all other countries

The BAS will be the analysis population. Statistical reports (descriptive statistics) will be provided including all parameters from Baseline, First documented procedure, Additional procedure, GFU and 12MFU, but due to data protection no data from the Adverse Event form. The benchmark reports will be listed in tabular form and, depending on the variable type, the statistical output will include numbers and percentages, mean  $\pm$  SD, Odds ratio with 95% CI for all available parameters.

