DAP by country	BAS incl.: --- excl.: ---	Baseline	-	X
Fluoroscopy time by country	BAS incl.: --- excl.: ---	Baseline	-	X

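### Country comparisons, country benchmark odds ratios and the AFEQT language test treat patients as independent although the plan assumes clustering by site, so their p-values are too small and their 95% CIs too narrow

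*SAP*

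**What the plan says.** - **Clustering in the sample size.** SAP 3.3 (and protocol 4.3) uses "Design effect = 1.2 (variance inflation due to cluster sampling design". SAP 3.1 expects 40 sites in 14 countries and 800–1000 patients; protocol 3.6 gives about 38 sites in 13 countries.
- **Country comparisons.** SAP 8.6.2: "Group comparison will be provided including non-parametric statistical tests and odds ratios with 95% CI (two-group comparison) for all parameters". The Appendix D list includes "DAP by country" and "Fluoroscopy time by country", both on the BAS at the final analysis. No specific test and no alpha are given.
- **Country benchmarks.** SAP 8.7 plans "Participating country vs. all other countries", with "Odds ratio with 95% CI for all available parameters". The reports are "designed to be used as quality control for the participating sites and to describe country differences".
- **AFEQT language test.** SAP 6.3.1 Step 1 compares baseline scores between validated and not validated versions with a two-sided Wilcoxon-Mann-Whitney test at 0.05, assumes the two patient groups have equal medical history, and adds: "Further predictors or confounders will not be considered". A significant result removes the not validated data from all further analyses; a non-significant one leads to merging.
- **Protocol 3.5** plans all AFEQT analyses for the overall sample and stratified by validated versus not validated version. It contains no exclusion rule.

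No analysis section of either document names a site effect, a random effect or a cluster-robust variance.

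**The concern.** Every patient at a site belongs to the same country, and language version follows country closely. With 40 sites in 14 countries, a country contrast rests on about three sites (40/14 = 2.9), yet the planned tests and intervals count 800–1000 independent patients. Ordinary differences between sites then enter the country or language contrast without entering its standard error.

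The documents themselves expect sites to differ. Protocol 3.6.1 does not select sites by experience. Protocol 4.4.3 says that the available sheath affects which veins can be reached and whether extra equipment is used. SAP 8.8 plans plots of DAP by site and of procedure time by site and operator. Fluoroscopy time is an efficiency parameter in SAP 8.3.2.

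Two things are at stake: how far the published country differences can be trusted, and whether QoL data are discarded because a few sites happen to score differently at baseline.

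**Working it through.** **1. The plan's own figure.** Table 1 follows n = DE × 1.96² × p(1−p)/d². For p = 0.2, d = 0.025 and DE = 1.2 this gives 1.2 × 3.8415 × 0.16/0.000625 = 1180.1, so 1181, as printed. Without the factor it would be 984. All 12 cells reproduce to within one patient, and only with 1.2. Clustering was therefore built into the size of the study.

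**2. Implied ICC.** ICC = (DE−1)/(m−1). With 800/40 = 20 patients per site, 0.2/19 = 0.0105. With 1000/40 = 25 per site, 0.2/24 = 0.0083. Larger values below are assumptions.

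**3. Actual error of a nominal 5% test when grouping is constant within site** (equal site sizes, no true group effect):
- Two groups: 2 × [1 − Φ(1.96/√DE)]. At DE 1.2: 1.96/1.095 = 1.789, giving 7.4%.
- 14 countries: P(χ²₁₃ > 22.36/DE). At DE 1.2: P(χ²₁₃ > 18.63) = 13.5%.
- ICC 0.05, 20 per site: DE = 1 + 19 × 0.05 = 1.95, giving 16% and 57%.
- Correct 95% CIs would be √DE times wider: 1.10 at DE 1.2 and 1.40 at DE 1.95.

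**4. Simulation** (2000 runs per row; 12 countries with 3 sites and 2 with 2; normal site effects; no country or language effect). Five of the 14 countries are assumed to use not validated versions. Kruskal-Wallis is assumed for the 14-country test. Monte Carlo standard error is at most about 1 percentage point.

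| Patients per site, ICC | 14 countries | Language test | One country v rest |
|---|---|---|---|
| 20, 0.0105 | 12.3% | 6.2% | 5.4% (odds ratio) |
| 25, 0.0083 | 13.0% | 7.1% | 7.0% (continuous) |
| mean 20, unequal, 0.0105 | 16.8% | 8.9% | 6.0% (odds ratio) |
| 20, 0.05 | 55.4% | 14.4% | 9.7% (odds ratio) |
| 25, 0.05 | 65.2% | 18.6% | 18.5% (continuous) |
| mean 20, unequal, 0.05 | 67.4% | 21.4% | 11.3% (odds ratio) |

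The odds-ratio rows use a 20% outcome with the ICC on the underlying continuous scale. The 18.5% is for a continuous outcome. An odds ratio would reach about that level only if 0.05 were the ICC on the observed binary scale. If the ICC of 0.05 lies between countries rather than sites, the language test (1000 patients) rejects 35.8%.

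**5. Site as the unit.** Comparing site means in the 800-patient settings, equal or unequal site sizes, gives 3.8% to 5.9% at every ICC tried from 0 to 0.2.

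**The case against.** - **The outputs are exploratory.** SAP 1.1, 8 and 8.5 describe the analysis as exploratory or descriptive with no hypotheses, and SAP 8 asks for 95% CIs to be read that way. SAP 8.7 calls the benchmarks descriptive and attaches no decision rule. This stands. A reader might infer that site differences will be formally declared to be country differences; the documents do not support that for the country comparisons or the benchmarks. The label does not, however, make a 95% interval cover 95%.
- **The larger error rates rest on inputs the plan lacks.** This also stands. No ICC is given, the 1.2 was set for recurrence or re-ablation rather than fluoroscopy time, DAP or AFEQT, and Kruskal-Wallis is only a plausible reading of SAP 8.6.2. A reader might take 55–67% as the plan's error rate; the documents support only the figures at design effect 1.2, where the two-group inflation is modest.
- **Language is not country.** A reader might conclude that five named countries would lose their QoL data. SAP 6.3.1 lists seven languages, Russian and Arabic among them, and nowhere maps them to countries. The link is an inference.
- **Site variation is displayed elsewhere**, in the site benchmarks and the SAP 8.8 box plots. True, but neither changes the country or language p-values and intervals.
- **Some cluster corrections do worse.** In a further simulation (40 sites of 25, 20% outcome, 20,000 runs), an independence GEE with the standard sandwich variance for one country against the rest rejected about 20% under the null with 3 sites and 31% with 2. The unadjusted odds ratio rejected 6–7% at design effect 1.2. This stands and limits the choice of remedy.

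**Conclusion.** The omission is real in all three places: the plan sizes the study for clustering and then ignores it where the grouping lies between sites. At the plan's own design effect, the nominal 5% becomes about 7% for two groups and about 13% for a 14-country test. At an assumed ICC of 0.05 it becomes about 14–19% for the language test (21% with unequal sites), 55–67% for the 14-country test, and 10–18% for a country-versus-rest odds ratio, depending on the ICC scale.

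For DAP, fluoroscopy time and the benchmarks, the harm is misleading p-values and intervals in exploratory output. For AFEQT Step 1 it is a data decision: an unclustered p<0.05 removes data that protocol 3.5 says will be analysed. The estimate for the main objective is a separate matter and is not touched by this point. The sizes rest on equal or moderately unequal site sizes, about three sites per country, and the assumed test, ICC and language grouping.

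**What to change.** - **DAP and fluoroscopy time by country (SAP 8.6.2, Appendix D).** Name the analysis: a linear mixed model on log values or ranks with site as a random effect and Kenward-Roger or Satterthwaite degrees of freedom, or a comparison of site means.
- **Country benchmarks (SAP 8.7).** Use a mixed logistic model with a site random effect and small-sample degrees of freedom, or a site-level comparison. Alternatively, show sites within country descriptively, without CIs. Do not use a standard sandwich GEE with two or three sites in one group. Site-versus-rest benchmarks can stay as they are.
- **AFEQT Step 1 (SAP 6.3.1).** Drop the rule by which an unclustered p<0.05 decides exclusion. Report overall and stratified by validated version, as in protocol 3.5. Any test that is kept should carry site and country random effects.

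The cost is SAP wording and standard SAS mixed-model procedures. Intervals widen, and with about three sites each some country estimates will be imprecise. Power to detect a real translation effect also falls. For a 0.3 SD shift with site and country ICC both 0.05, a test with country as the unit had 42% power in simulation, against 85% for the unadjusted test, whose false-positive rate was itself 42%. Since non-significance currently leads to merging, stratified reporting is safer than any test-based gate.
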